1.0 OBJECTIVES

1.1 Primary Objective

To test the association of hepatic iron content (HIC) measured with the newly developed 1.5T R2*-UTE technique and HIC quantified by liver biopsy in subjects with iron overload.

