Figure 2 shows the 95% confidence interval for the T2* fit derived from the precision calculations and overlaid on the Bland–Altman plot in Fig. 1B. The simulation (red curve) shows that there is a nonlinear change in precision. This change is not easily recognized in the low to moderately iron-overloaded population (<15 mg/g), and therefore may have been missed by other investigators. The simulation confirmed our experimental observation of a large imprecision for higher iron overload with the standard R2*-GRE method. Other researchers have reported higher HIC values using standard R2*-GRE, but these data points demonstrated larger errors or deviated from the linear regression line.^{16;59} Interpretations of these findings focus on the multi-exponential signal decay or nonlinear relationship between HIC and R2*-GRE, respectively, in highly overloaded areas of the liver.⁵⁹ Because the results of our fit precision simulations and experimental data are in concordance, we conclude that the fit imprecision at

higher HIC is the major source of inaccuracy between HIC and R2*-MRI while measuring iron overload in patients; other potential sources of error may be negligible.

Our simulation model gives the upper limit on the R2* fit precision obtained with a specific MR sequence (e.g., R2*-GRE). With the proposed R2*-UTE sequence, which yields optimized precision for high R2* values too, we can characterize other potential factors impacting the correlation between HIC and R2*. Although multi-exponential or nonlinear behavior cannot be ruled out by using current methods, a more accurate quantification of large R2* species can help determine the true correlation between HIC and R2*-MRI and ultimately the distribution of hepatic iron stores in patients with massive iron deposition.

[figure not shown]

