9.1 Power and Accrual

Based on MRIRON study, we found that the correlation between R2*-GRE and HIC is 0.56 for patients with HIC > 15 mg Fe/g. The new R2*-UTE technique is expected to perform better for measuring high HIC values. Therefore, instead of testing if the r_{UTE} is different from zero, here we wish to test if the r_{UTE} is greater than 0.6. The one-sided testing hypotheses can be formulated as below: the null hypothesis $H_0: r_{UTE} \leq 0.6$ against the alternative hypothesis $H_a: r_{UTE} > 0.6$ we assume the true r_{UTE} to be 0.8. The study will be designed to have a significance level at $\alpha = 0.05$ and power at $1 - \beta = 0.8$. Although the parameter space for H_0 is large, to estimate the required sample size, we only need to consider the scenario that requires the largest sample size, which is: $H_0: r_{UTE} = 0.6$ v.s. $r_{UTE} = 0.8$. Based on a one-sided test, this design requires **41** liver biopsy samples.

We hope to accrue about 10-12 liver biopsies per year, so it will take approximately 4 years to achieve the desired sample size. Study subjects will be allowed to participate on the study only once in order to avoid potential bias introduced by repeat measurements on the same patient. There is a small chance that the liver biopsy specimen may be deemed inadequate due to technical sampling reasons. In this case, we will amend the protocol and continue patient accrual until we have obtained 41 evaluable liver biopsy specimens.

Approximately 20% of patients with iron overload have HIC values above 25 mg Fe/g, placing them in the category of massive iron overload. Because we aim at obtaining 41 liver biopsies for the analysis of the primary objective, we estimate that approximately 200 patients will undergo MRI testing with both R2*-GRE and R2*-UTE.

Healthy volunteers will be necessary for sequence development, and later for testing the robustness and repeatability of the UTE sequences. We estimate that approximately 35 healthy volunteers will be needed for sequence development and implementation.

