9.2 Statistical Analysis

For the primary objective: *To explore the association of hepatic iron content (HIC) measured with the newly developed 1.5T R2*-UTE technique and HIC quantified by liver biopsy in subjects with iron overload.*

The relationship of HIC measured with 1.5T R2*-UTE and quantified by liver biopsy in subjects with iron overload will be explored graphically. If the linear relationship exists, the Pearson's correlation between the HIC measured with 1.5T R2*-UTE technique and the HIC quantified by liver biopsy will be calculated and its 95% confidence interval (CI) will also be reported. If the correlation is sufficiently high, i.e., the lower bound of the 95% CI exceeds 0.7, a simple linear regression model will be established for the HIC prediction. The 95% prediction bounds will be established. If more complicated pattern shown graphically, appropriate model will be developed to describe the relationship.

For the secondary objectives: *To explore the relationship 1) between 1.5T R2*-UTE and 1.5T R2*-GRE measurements in healthy volunteers and in subjects with iron overload and 2) between 1.5T R2*-UTE measurements with iron studies (serum iron and transferrin saturation) in subjects with iron overload.* Analyses will be implemented similarly as the analyses planned in the primary objective to explore the relationships. Pearson's correlation will be used if there is graphical evidence of linear relationship, similarly to the Primary Objective. 95% confidence interval (CI) will also be reported. If correlation is sufficiently high, a simple linear regression model will be developed and the 95% prediction bounds will be established. If more complicated pattern shown graphically, appropriate model will be developed to describe the relationship.

Objectives 1.3.1, 1.3.2, 1.3.3, 1.3.4, and 1.3.5 were classified as exploratory since they do not directly support the future implementation of the 1.5 R2*-UTE technique, and the gathering of the information from variables within these objectives is not yet clear in the near future but may ultimately generate additional hypotheses for future investigation. The purpose of the exploratory objectives is to (1) evaluate how well the R2*-UTE and the R2*-GRE signals correlate in subjects where the R2*-GRE does not fail. The analyses will provide the evidence of whether the R2*-UTE technique can replace the R2*-GRE technique even in the lower HIC

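### Section 9.2 computes the primary correlation only if a plot is judged linear and never states the r > 0.6 test on which Section 9.1 sizes the study

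*Combined protocol and SAP*

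**What the plan says.** - **Section 1.1** sets the primary objective: "To test the association of hepatic iron content (HIC) measured with the newly developed 1.5T R2*-UTE technique and HIC quantified by liver biopsy".
- **Section 9.1** turns this into a hypothesis: "here we wish to test if the r_{UTE} is greater than 0.6", and "we assume the true r_{UTE} to be 0.8". With alpha 0.05 and power 0.80, "Based on a one-sided test, this design requires" 41 biopsies. Nothing in 9.1 makes the test conditional. Section 3.4 stops enrolment when that number of biopsies is reached.
- **Section 9.2** is the operative analysis text, and the synopsis repeats it. The data are plotted first. Pearson's r and its 95% interval follow under the condition "If the linear relationship exists". If the lower limit exceeds 0.7, a linear prediction model is built. In the other case, "If more complicated pattern shown graphically, appropriate model will be developed to describe the relationship".
- **Section 2.7**, on the relation between R2* and HIC: "Although multi-exponential or nonlinear behavior cannot be ruled out by using current methods".
- Section 9.2 and the synopsis analysis text describe the primary aim as exploring the association, whereas Sections 1.1 and 9.0 speak of testing it.

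**The concern.** The condition in Section 9.2 is a written rule, so the gap cannot be filled simply by reading 9.1 into it. The plan gives no criterion for linearity, does not say who judges the plot, names no alternative model, and attaches no test, threshold or alpha to the non-linear branch.

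If the plot is judged curved, the study can finish with 41 biopsies and no prescribed answer to the question that set that number. A curve would be developed on the same 41 points with no stated standard for calling it adequate. The intended use is as an alternative to biopsy, so the acceptance rule should not rest on an undefined visual judgement.

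**Working it through.** **1. The plan's own figure.** Inputs from Section 9.1: null 0.6, alternative 0.8, one-sided alpha 0.05, power 0.80. By Fisher's z:

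n = [(1.645 + 0.842) / (atanh 0.8 − atanh 0.6)]² + 3 = [2.487 / (1.0986 − 0.6931)]² + 3 = 40.61, rounded up to **41**.

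This reproduces the plan. Power at 41 is Φ(0.4055 × √38 − 1.645) = 0.804. The null is rejected when observed r is at least tanh(0.6931 + 1.645/√38) = 0.744.

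**2. The only rule in Section 9.2.** A two-sided 95% lower limit above 0.7 needs observed r of at least tanh(0.8673 + 1.960/√38) = 0.829. At true r = 0.8 and n = 41 the probability is Φ((1.0986 − 0.8673) × √38 − 1.960) = 0.30. For 80% probability, n = [(1.960 + 0.842)/0.2313]² + 3 = 149.7, about 150. This is a different and much harder criterion than the one the study was sized for.

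**3. The two branches side by side.**

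| | Plot judged linear | Plot judged curved |
|---|---|---|
| Pearson's r and 95% CI | yes | not prescribed |
| One-sided test of 0.6 (Section 9.1) | not stated | not stated |
| Decision rule | lower limit > 0.7 | none |

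**4. How often the correlation might be skipped.** The plan gives no linearity criterion, so a stand-in is needed: the plot counts as curved when a quadratic term has p < 0.05. All settings below are assumptions.

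*Calibration-type model.* There are 6,000 trials of n = 41. Biopsy HIC h is lognormal (median 25 mg Fe/g, log-SD 0.45), with or without limiting it to 3–68. UTE = h − s·h²/120 plus constant noise. The slope at h = 60 is 1 − s, so s = 0.5 and 0.8 cut it by 50% and 80%.

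- Truly linear (s = 0): skipped in about 5%, as the 0.05 level of the stand-in implies.
- Curved, noise set so that r would be 0.8 if linear (the plan's value): skipped in 8–20%. Median Pearson r is about 0.56–0.70, and the Section 9.1 test rejects in only 2–29%.
- Curved with s = 0.8, noise set so that r would be 0.90 if linear: without limits on HIC, 35% skipped and 35% rejection; limited to 3–68, about 25% and 61%.
- Across all curved settings: skipped in about 8–36%.

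*Second model.* There are 8,000 trials of n = 41, with a normal predictor and quadratic curvature.

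| Truth | Test run | Run and rejects | Rejects if always run |
|---|---|---|---|
| Linear, r = 0.80 | 95% | 0.78 | 0.82 |
| Mild curvature, Pearson r 0.79 | 81% | 0.63 | 0.78 |
| Stronger curvature, Pearson r 0.80 | 20% | 0.17 | 0.82 |

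Under the null (linear, r = 0.6), rejection given that the test is run was 0.053 with this stand-in and 0.055 with a stricter one (p < 0.20). It was 0.054 if the test is always run.

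**The case against.** Checking linearity before using Pearson's r is ordinary practice, and under curvature a forced Pearson test can mislead. At the plan's own r = 0.8, the curved cases above reject in only 2–29%, so the test would often fail for a relation that is real. That stands. It argues for reporting the curved fit beside the test, but not for leaving the primary hypothesis without any prescribed analysis.

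Linearity is also the expected case. Section 2.6 reports correlations of 0.96–0.98 with a linear fit for R2*-GRE. Section 2.7 attributes most of the inaccuracy at high HIC to fit imprecision and says only that non-linearity cannot be excluded. A reader might infer that the protocol predicts curvature; it does not.

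A reader might also infer that someone who has seen the results could pick the branch to suit them, or that type I error is inflated. The documents do not support either. This is a single-group calibration study with no allocation to conceal. Section 4.2 blinds the image examiners to biopsy results, and nothing is said about who reads the plot. The simulated null rejection rate stays near 0.05. A subjective visual rule could behave differently from the quadratic stand-in, but that is untested.

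Finally, Sections 9.0 and 9.1 do not make the test conditional on a plot, so it would be too strong to say that it would certainly be dropped. What holds is that Section 9.2 does not prescribe it.

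**Conclusion.** The concern holds as a specification gap between Sections 9.1 and 9.2. The test that justifies 41 biopsies does not appear in the analysis section. The correlation it rests on is conditional on an undefined visual judgement, and the other branch has no success rule. The sample-size arithmetic itself is correct.

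The consequence is a possibly undefined primary result and lost power; no demonstrated bias is involved. Its size depends heavily on the assumed curvature, noise, HIC range and stand-in for the visual check: about 5% of trials skipped under linearity, 8–36% under curvature in the calibration-type model, and 19–80% in the second model (100% minus the 81% and 20% run). These figures illustrate the issue and do not forecast this study. The 0.6 versus 0.7 discrepancy does not depend on simulation: at true r = 0.8 the 9.2 rule is met about 30% of the time, against 80% for the 9.1 test.

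**What to change.** In Section 9.2 and the synopsis:

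1. State that the one-sided 0.05 test of r > 0.6 is run on all evaluable UTE–biopsy pairs and reported with the confidence interval, whatever the plot shows. The plot then serves only to choose the form of the calibration model.
2. If a curved calibration is adopted, also report the correlation between biopsy HIC and leave-one-out predicted HIC, judged against the same threshold (0.6, one-sided). Label it supportive: the form is chosen from the same data, and leave-one-out prediction does not account for that choice.
3. Reconcile the 0.7 rule with the 0.6 test by saying what each decides. If the 0.7 limit is meant as the success criterion, the sample size needs revisiting (about 150 biopsies for 80% at true r = 0.8).
4. Use one verb, test or explore, for the primary objective throughout.

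The cost of items 1, 2 and 4 is a few sentences and little analysis work; the sample size stays at 41 with power 0.804 under the plan's assumptions. The downside is that Pearson's r understates a curved relation, and at the assumed r = 0.8 the loss of power can be large. The plan should therefore say that a failed test is to be read alongside the curved fit.

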2.6 Calibration of the R2*-GRE Technique – the MRIRON Study

Since 2005, we have investigated MR quantification of patients with transfusional iron overload at St. Jude Children's Research Hospital. As part of the institutional MRIRON trial,³³ we studied 43 research participants with iron overload [sickle cell anemia (32), β -thalassemia major (6), and bone marrow failure (5)] who completed liver biopsy within 30 days of the R2*-GRE examination. Their median age was 14 years, median transfusion duration 15 months, average (\pm SD) serum ferritin 2718 ± 1994 ng/mL, and average HIC 10.9 ± 6.8 mg Fe/g dry weight liver. Our R2*-GRE sequence acquired 20 axial liver images with increasing echo times (TE=1.1–17.3 ms) in a single breath-hold. The signal intensity decay over the 20 images in each pixel was measured as a function of TE and quantitative T2* ($T2^*=1/R2^*$) maps were calculated with an exponential fit after background subtraction. Three independent reviewers performed ROI analysis on T2* maps, and their results were in excellent agreement (intraclass correlation coefficient = 0.98). We found serum ferritin and R2*-GRE to be weakly but significantly associated (correlation coefficients 0.41–0.48, all $P < .01$) and R2*-GRE to be strongly associated with HIC (correlation coefficients 0.96–0.98, all $P < .0001$). This high correlation confirmed results of prior reports,^{11, 15} calibrated R2*-GRE measurements, and demonstrated the clinical feasibility of predicting HIC using R2*-MRI. Figure 1 summarizes the measured data and HIC prediction curve.

[figure not shown]

Figure 1: MRIRON study results: R2*-GRE vs. HIC. (A) Correlation between measured R2* values and HIC biopsy results with linear regression line (solid line) and 95% prediction limits (dashed lines). (B) Bland-Altman plot indicating the mean difference between HIC values predicted by R2*-GRE and biopsy (solid line) and the upper and lower 95% limits of agreement between the two measurements (dashed lines). The uncertainty of the prediction for higher HIC (>15mg Fe/g dry weight) is discussed in the text.³³

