If an exam based on a 1.5T R2*-GRE measurement that was analyzed using clinical criteria as established in the AIM09 clinical practice protocol fails according to established criteria (failed or non-converging fit precision in more than 10% of the voxel prescribed in the ROI), a liver biopsy is clinically indicated and will be performed (if recommended by the treating clinician) within 30 days of the MRI exam. In other words, in this case, the current R2*-GRE method fails to provide a predicted HIC value because not enough pixels in the selected ROI capture the MR signal decay. In our experience, the insufficient fit corresponds to increased concentrations of iron in the hepatic tissue, and the threshold at which failed fits are seen in individual pixels begins at about 500 Hz and accentuates above 900 Hz, which corresponds to an HIC of ~ 15 and 25 mgFe/g, respectively.

Healthy volunteers will undergo R2*-UTE and R2*-GRE studies at both, 1.5 and 3T MRI field strengths. No blood work or liver biopsy will be performed on healthy volunteers.

The result of the liver R2*MRI will be shared with the participants' primary clinician and the decision to pursue a liver biopsy will be made by the treating primary clinician. If the participant's primary clinician is from an outside institution (such as in the case of the adult participants), the MIDAS study staff will contact the primary treating clinician and inform him of the MRI results, and a copy of the report will also be mailed or faxed to his office. The primary clinician will review the MRI results and will communicate back with the MIDAS investigators to inform if a liver biopsy is warranted or not. If a liver biopsy is indeed indicated and requested by the treating clinician, an appointment will be scheduled to perform the liver biopsy. Biopsies needed for subjects 26 years of age and older will occur at an adult facility (Regional One Health or other adult hospital), patients 25 or younger will have their liver biopsies performed at St. Jude.

[figure not shown]

Figure 3: Flow diagram for the screening and testing of subjects in the MIDAS study.

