9.0 STATISTICAL CONSIDERATIONS

This is a non-therapeutic, prospective study aimed to develop a novel R2*-UTE imaging sequence technique to non-invasively and accurately estimate high hepatic iron content (HIC) values (≥ 25 mg Fe/g). The current standard management procedure for patients at risk of iron overload at St. Jude is to estimate their (HIC) by the calibrated R2*-GRE imaging technique, which becomes unreliable when HIC is greater than 25 mg Fe/g. Therefore, the success of the study will provide better monitoring and guidance to the clinical management of patients with massive iron overload.

The primary objective is to test the association of hepatic iron content (HIC) measured with the newly developed 1.5T R2*-UTE technique and HIC quantified by liver biopsy in subjects with iron overload. The liver biopsies will be obtained as indicated by good clinical management practice, and it is expected that most research participants who will receive the liver biopsy will have an inconclusive result by the R2*-GRE method. The iron quantification assessed in liver biopsies will be correlated with the R2*-UTE signals. If the correlation is sufficiently high, then a statistical model relating HIC by R2*-UTE and liver biopsy values will be established, as was done for R2*-GRE.³²

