cases. (2) understand the relationships among a set of variables measured, Similar analyses will be implemented similarly to the analyses implemented in the primary objective.

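### Section 9.2 promises evidence on replacing GRE with UTE at lower HIC, but plans no summary of the difference in reported HIC and names no UTE calibration for that range

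*Combined protocol and SAP*

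**What the plan says.** The exploratory paragraph of section 9.2 gives as its first purpose to "evaluate how well the R2*-UTE and the R2*-GRE signals correlate in subjects where the R2*-GRE does not fail". It then adds: "The analyses will provide the evidence of whether the R2*-UTE technique can replace the R2*-GRE technique even in the lower HIC" cases. The method is one line: "Similar analyses will be implemented similarly to the analyses implemented in the primary objective".

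The primary analysis referred to is a plot, then Pearson's r with a 95% CI if the plot looks linear, then a simple linear regression with 95% prediction bounds if the lower confidence bound exceeds 0.7. If the plot is not linear, another suitable model is to be developed. For the secondary objectives the steps are the same, but how high r must be is not given as a number.

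The same paragraph is modest elsewhere. It says that the exploratory information "may ultimately generate additional hypotheses for future investigation" and that these objectives give no direct support for bringing 1.5T UTE into use.

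The UTE-GRE comparisons among the exploratory objectives are 1.3.2 (1.5T UTE with 3T GRE) and 1.3.3 (3T with 3T). The 1.5T UTE with 1.5T GRE comparison is secondary objective 1.2.1. The rule for a failed scan in section 5.1 is written for 1.5T GRE; it begins "If an exam based on a 1.5T R2*-GRE measurement that was analyzed using clinical criteria".

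On where the biopsies will fall, section 9.0 states that "it is expected that most research participants who will receive the liver biopsy will have an inconclusive result by the R2*-GRE method".

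**The concern.** Whether one method can replace another depends on whether patients would be given a materially different HIC. Reported HIC has two parts: the R2\* signal and the calibration that converts it. The plan compares only signals. A high r does not show that two measurements agree. A regression of one R2\* on the other says nothing about the conversion.

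The conversion matters because the UTE calibration may contain few biopsies in the range where GRE works (section 9.0, quoted above). Section 2.7 also allows for departures from a straight line: "Although multi-exponential or nonlinear behavior cannot be ruled out by using current methods". The plan does not say whether UTE will use its own biopsy calibration at lower HIC or the existing GRE one.

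The team has used the missing kind of summary before. Figure 1 in section 2.6 includes a "Bland-Altman plot indicating the mean difference between HIC values predicted by R2*-GRE and biopsy", with limits of agreement. Section 9.2 plans nothing like it for UTE against GRE.

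At stake is a secondary or exploratory conclusion: a high r could be offered as evidence for replacement without showing whether reported HIC would change.

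**Working it through.** **1. The plan's own figure.** The only powered number is for the primary test (section 9.1: r = 0.6 against 0.8, one-sided alpha 0.05, power 0.80). n = ((1.645 + 0.842) / (atanh 0.8 − atanh 0.6))² + 3 = (2.487 / 0.4055)² + 3, about 40.6, rounded up to 41. It reproduces, and this point does not touch it. No sample size or precision is given for UTE against GRE.

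**2. What a correlation rule would let through.** Section 9.1 expects about 200 patients scanned with both techniques and about 20% above 25 mg Fe/g. Assume that GRE is readable in the rest: 0.8 × 200 = 160 pairs. Assume also that the 0.7 rule carries over. The smallest r that passes is tanh(atanh 0.7 + 1.96/√157) = tanh(0.867 + 0.156) = 0.771.

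With equal variances and no bias, the SD of the differences is SD × √(2(1 − r)) = 0.676 × SD, and the limits of agreement are ±1.96 times that:
- SD 6.8 mg Fe/g (MRIRON, section 2.6): 4.60, limits ±9.0 mg Fe/g.
- SD 4.0 mg Fe/g (assumed for a narrower, lower range): 2.70, limits ±5.3 mg Fe/g.

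For scale, section 2.6 treats GRE deviations of up to ±6 mg Fe/g at 15–25 mg Fe/g as a limitation. That is background, not an acceptance limit.

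**3. What the regression adds.** Simulated: 160 pairs, R2\* uniform over 100–900 Hz, noise SD 10 Hz in both methods. r is 0.998 whether UTE reads true or 20% high (mean difference 100 Hz). The planned regression would show this, with slope 1.20. Calibrating UTE on its own biopsies would then remove it: the change in predicted HIC is 0. A uniform R2\* bias is therefore not the gap. The gap is the step from R2\* to HIC.

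**4. The HIC step, with both methods reading the same true R2\*.** Simulated, 2,000 runs per setting. Inputs:
- Section 5.1 gives 500 Hz at about 15 and 900 Hz at about 25 mg Fe/g. Two relations pass through both: a straight line, R2\* = 40 × HIC − 100, and a mild curve, R2\* = 500 × (HIC/15)^1.151. Extending either beyond these points is an assumption.
- GRE calibration: 43 biopsies, HIC mean 10.9, SD 6.8 (section 2.6), truncated to 3–25.
- UTE calibration: 41 biopsies, of which 8 lie uniformly in 5–25 and 33 in 25–60 mg Fe/g (assumed).
- Biopsy CV 10% and R2\* noise 5% (assumed); 160 comparison patients distributed like the GRE calibration set.

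| How UTE R2\* becomes HIC | True relation | Mean difference, UTE − GRE, mg Fe/g (95% of runs) | Runs beyond 1 mg Fe/g |
|---|---|---|---|
| GRE calibration shared | either | 0 | – |
| Own log-log fit | curved | 0.0 (−0.95 to 0.95) | 4–5% |
| Own straight line | straight | 0.4 (−1.4 to 2.2) | 31% |
| Own straight line | curved | 1.2 (−0.6 to 3.2) | 57% |

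The signal comparison looks the same throughout: r = 0.99 and slope 0.99. Moving 16 more UTE biopsies into 15–25 mg Fe/g lowers the two straight-line results to about 0.2 and 0.9. Varying the low biopsies from 12 to 0 gives 0.3 to 1.2 (straight) and 0.9 to 3.0 (curved). The 1 mg Fe/g yardstick is mine and is not in the documents.

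**The case against.** The strongest reply has four parts.

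- **The regression shows bias.** For R2\* it does, as step 3 confirms. A reader might infer that the plan would miss a UTE signal that over-reads, and that patients would then get wrong HIC values. The documents do not support that: the planned regression would show the shift, and calibration would absorb a uniform one.
- **Two separate calibrations are assumed.** No section requires UTE to use a calibration built mainly on high-iron biopsies at lower HIC. If the two R2\* values agree there, the GRE calibration could serve and the mean difference is about 0. This stands. It narrows the point to the conversion being unstated.
- **The curved case skips a planned step.** Section 9.2 provides for another model if the plot is not linear, and a log-log fit removes the mean difference. This stands too, with the caveat that the fitted form was the true one and that mild curvature may not be visible in a plot. The assumed biopsies also lean high: in SWiTCH (Table 1), 64 − 24 = 40 of the 64 patients at or above 15 mg Fe/g were below 25.
- **It is exploratory.** The paragraph says so, and this limits the weight of the point. It does not remove a sentence in the same paragraph that promises the evidence on replacement.

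It is also fair that a UTE-GRE difference cannot show which calibration is wrong; only biopsies in the lower range can.

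**Conclusion.** The point holds as a cheap improvement. The method stated in section 9.2 cannot answer the replacement question stated there. It measures correlation of signals, has no summary of the difference in reported HIC and no acceptable difference, and leaves the UTE conversion at lower HIC open. The sentence is also attached to 3T GRE objectives, although the matching comparison is 1.2.1.

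The size is illustrative. With 8 of 41 UTE biopsies below 25 mg Fe/g, the mean predicted-HIC difference runs from about 0 (shared calibration, or a well-chosen curved model) to about 1.2 mg Fe/g (separate straight lines, mildly curved relation). The r of 0.77 depends on 160 usable pairs and on the 0.7 rule carrying over.

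A reader might go further and infer that UTE will report HIC too high in lower-iron patients. The documents do not support that. The calibration, the biopsy distribution and the shape of the relation are all unknown, and every simulated interval in the table includes zero. What is shown is that the planned outputs would not reveal the difference either way.

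**What to change.** In section 9.2:

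1. Attach the replacement question to objective 1.2.1.
2. For 1.5T UTE against 1.5T GRE, in participants whose GRE did not fail, state which calibration converts UTE R2\* to HIC. Report the mean difference in predicted HIC with 95% CI and Bland-Altman 95% limits of agreement. Keep r and the regression as descriptive.
3. Either state beforehand the HIC difference regarded as acceptable, which the investigators must set, or reword the replacement sentence as hypothesis-generating, in line with the rest of its paragraph.

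The cost is some wording and a little extra analysis of data already being collected. The expected numbers can support it: with 160 pairs and an assumed SD of the differences of 2 mg Fe/g, the CI half-width is 1.96 × 2/√160 = 0.31 for the mean and 1.96 × 2 × √(1/160 + 1.96²/(2 × 159)) = 0.53 mg Fe/g for each limit, taking the calibrations as fixed. The downside is that the result is conditional on those calibrations. The primary analysis and the 41 biopsies do not change.
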